2.5.2. Analysis of neuroimaging data

fMRI data will be analyzed using Statistical Parametric Mapping software running under the MATLAB® environment (SPM12) [52]. Preprocessing steps will include realignment and geometric unwarping using magnitude and phase images from the field map, slice-time correction, echo planar (EPI) co-registration to the participant's segmented, skull-stripped, bias-corrected T1-weighted image, normalization to Montreal Neurological Institute space with resampling to 2 mm isotropic using 4th degree B-spline interpolation, and smoothing with a 6 mm isotropic full width at half-maximum Gaussian kernel. Each run of EPI data will be evaluated for motion: (a) the degree of linear movement will be assessed and classified (threshold = 3 mm linear movement in orthogonal planes), and (b) the ART toolbox (Artifact Detection Tools; www.nitrc.org/projects/artifact_detect) will be used to detect outlier volumes based on image intensity relative to the global mean image (threshold = 3.5xSD) and motion (threshold = 0.8 mm, measured as scan-to-scan movement). Individual runs will be excluded if they show either (a) >3 mm linear movement and >10% outliers, or (b) >20% outliers.

For subject-level analyses, a general linear model (GLM) either with regressors of high-calorie foods, low-calorie foods, and objects (food cue paradigm) or with regressors of successful stop trials and failed stop trials (SST) will be specified. Regressors will be placed at the onset of each condition within a block, convolved with the canonical hemodynamic response function. Global mean signal and motion outliers will be entered as nuisance regressors. Following GLM estimation, the primary contrast (high-calorie foods versus objects, successful versus failed stop trials) will be computed at the single-subject level to estimate condition effects at every voxel, separately for each session (fasted/fed). For subsequent group-level analysis, we will use a factorial design with baseline versus 4-week contrasts to examine changes in brain activation

following oxytocin treatment in a-priori defined regions of interest (ROIs, food cue paradigm: VTA, OFC, anterior insula; SST: dlPFC, dACC, preSMA). For mediation analyses, beta values will be extracted from subject-level contrast images for clusters within a-priori ROIs that meet family-wise error rate correction ($p < 0.05$) using Marsbar software [53]. We will also analyze activation in additional reward-related food motivation and impulse control-related brain regions and the whole brain (applying α -error correction procedures). Moreover, we will examine activation in the hypothalamus as a brain region responsible for energy homeostasis.

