2.4.8. Neuroimaging

MRI scanning takes place on an FDA-approved 3T Skyra scanner (Siemens/Erlangen/Germany). We perform whole-brain functional fMRI using a gradient-echo EPI pulse sequence (33 contiguous oblique-axial slices angled 30° from the AC-PC axis, 4 mm thick, TR/TE = 2000/30 ms, flip angle = 90°, FOV = 200x200 mm, 120 total images per run).

- Food cue paradigm [42] – before (fasted state) and after (fed state) a standardized meal (see 2.4.6.): Participants view 100 high-calorie food stimuli (50% sweet/50% savory), 100 low-calorie food stimuli, 100 non-food object stimuli, and 100 fixation stimuli in a block design (5 runs, 4 minutes/run, 3 seconds/stimulus, 5 images/block, 16 blocks/run, images presented only once). Participants also rate a selection of food stimuli on valence and caloric content. The primary variable of interest is brain activation to high-calorie food stimuli compared to non-food stimuli.
- Stop-Signal Task (SST) [45,46] – fasted state: Participants are instructed to manually respond to visual go signals (circles) as fast and accurately as possible (within 3 seconds) but withhold their response when a stop signal (X) appears (25% of all trials, randomly selected, stop-signal delay following staircase-tracking algorithm). Trials are presented in a block design [64

trials/block, 3 blocks] following task practice outside the scanner. The primary variable of interest is brain activation to successful compared to failed response inhibition.

In addition to functional tasks, we acquire structural T1-weighted MRI images (MPRAGE sequence) for co-registration between structural and functional datasets. On a subset of participants (for whom scanning time allows), the Multi-Source Interference Task (an fMRI task reliably activating the cognitive control network involved in inhibiting task interference) [47], multi-echo T2-weighted MRI images, diffusion-weighted images, and resting state fMRI EPI images are acquired for further exploratory investigation of cognitive control, hypothalamic gliosis, white matter tractography, and functional connectivity.

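### The fMRI run-exclusion rule normally keeps runs with large gradual head movement, and the stated subject-level model lists no movement parameters to account for it.

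*Combined protocol and SAP*

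**What the plan says.** All of this is in section 2.5.2 of the combined protocol and SAP unless stated.

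- **Preprocessing** includes realignment and field-map unwarping, so movement estimates for every volume will exist.
- **Gross movement:** "the degree of linear movement will be assessed and classified (threshold = 3 mm linear movement in orthogonal planes").
- **Outlier volumes:** the ART toolbox flags a volume either on image intensity (3.5 SD relative to the global mean image) or on "motion (threshold = 0.8 mm, measured as scan-to-scan movement").
- **Run exclusion:** "Individual runs will be excluded if they show either (a) >3 mm linear movement and >10% outliers, or (b) >20% outliers".
- **Nuisance terms in the subject-level model:** "Global mean signal and motion outliers will be entered as nuisance regressors". No other nuisance term is listed.
- **Task terms:** "Regressors will be placed at the onset of each condition within a block, convolved with the canonical hemodynamic response function". No duration is given.

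Section 2.4.8 gives the acquisition as "TR/TE = 2000/30 ms" with "120 total images per run", and the food-cue task as "5 runs, 4 minutes/run, 3 seconds/stimulus, 5 images/block, 16 blocks/run, images presented only once".

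The contrasts from this model go into the group-level activation analysis. They also supply the beta values for the mediation analyses in section 2.5.3. No comparison of movement between arms or visits is planned.

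**The concern.** The 3 mm limit never acts alone. It works only together with the outlier percentage, and the motion part of the outlier test sees abrupt movement, not slow movement. A participant who sinks or rotates gradually by several millimetres can pass both tests. Such a run has few or no outlier regressors, and the listed model contains nothing else that follows the movement.

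Realignment and unwarping remove part of the effect of movement on the signal, but not necessarily all of it. What remains goes into the residual and makes each participant's contrast noisier. If movement changed between baseline and week 4 differently in the two arms, it could also look like a drug effect, and the plan has no report that would reveal this.

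The wording of the nuisance sentence raises a second issue. If the global mean time course itself is a regressor, each regional effect becomes relative to the brain-wide response. That matters because Aim 2 predicts falls in reward and homeostatic regions and rises in control regions.

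**Working it through.** **1. Run length (the plan's own figure).** 4 min × 60 / 2 s = 120 volumes. From the block structure, 16 × 5 × 3 s = 240 s, and 240 / 2 = 120. The stated 120 images per run is reproduced.

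**2. Exclusion thresholds.** 10% of 120 = 12, so rule (a) needs at least 13 outliers in addition to movement above 3 mm. 20% of 120 = 24, so rule (b) needs at least 25.

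**3. What gradual movement does to the rule.** There are 119 scan-to-scan steps.

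- A 3 mm drift is 3 / 119 = 0.025 mm per step.
- A drift of 0.05 mm per step totals 0.05 × 119 = 5.95 mm.
- A 10 mm drift is 10 / 119 = 0.084 mm per step.

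All are far below 0.8 mm. In simulated smooth drifts (1,000 runs per scenario), every run with 3.5 mm or 6 mm of total movement passed the motion rule, as did 98–99% of runs with 10 mm. Intensity flags were not simulated and could still catch some runs.

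**4. How often this might happen.** The documents give no movement data. For an assumed random walk on one axis, the share of runs above 3 mm is:

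| SD per scan (assumed) | Peak-to-peak range | Displacement from first scan |
|---|---|---|
| 0.05 mm | 0% | 0% |
| 0.10 mm | 2% | 1% |
| 0.15 mm | 21% | 12% |
| 0.20 mm | 53% | 31% |
| 0.30 mm | 92% | 65% |

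The answer depends on the assumed step and on how the 3 mm is measured, so no single frequency is defensible.

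**5. What a movement regressor buys.** One 120-volume run was simulated with a high-calorie minus object contrast. Assumptions: noise SD 1%, residual movement signal 0.05–0.30% per mm, and one movement regressor. The contrast SD without → with the regressor was:

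| Drift, signal per mm | No high-pass filter | Assumed 128 s filter |
|---|---|---|
| 3.5 mm, 0.10% | 0.256 → 0.257 | 0.266 → 0.280 |
| 3.5 mm, 0.30% | 0.277 → 0.255 | 0.277 → 0.271 |
| 6 mm, 0.30% | 0.313 → 0.259 | 0.311 → 0.276 |
| 10 mm, 0.30% | 0.426 → 0.258 | 0.391 → 0.275 |

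The largest gain is 1 − 0.258/0.426 = 39%. The worst row is a loss of 0.280/0.266 − 1 = 5%. Mean contrasts stayed near the true 0.25 in both models, so movement unrelated to condition and arm added noise, not bias.

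**6. Cost of six parameters.** Allowing 8 degrees of freedom for the terms already in the model (assumed) leaves 120 − 8 = 112, and six parameters leave 106. Ignoring collinearity with the task, the variance ratio is (1 − R²) × 112/106, where R² is the share of residual variance that movement explains. It breaks even at R² = 6/112 = 5.4%. Below that there is a small loss, at most 112/106 − 1 = 6% in variance.

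**7. If the global mean time course is entered.** Assume a true regional drug effect of −0.15 and a region that shares the global signal with unit weight. The estimate then tends to the regional change minus the global change.

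| Drug change in global response (assumed) | Regional minus global change | Simulated with global term | Simulated without |
|---|---|---|---|
| 0 | −0.15 | −0.141 | −0.136 |
| −0.02 | −0.13 | −0.142 | −0.163 |
| −0.05 | −0.10 | −0.092 | −0.138 |
| −0.10 | −0.05 | −0.045 | −0.141 |

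With no drug effect on the global response, the estimate was essentially unchanged and its SD fell from 0.301 to 0.253.

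**The case against.** Several points on the other side stand.

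- Realignment and unwarping already act on slow drift. Where little movement signal remains, six extra regressors give no gain or a small loss.
- The trial is randomized and double-blind, and section 2.4.6 holds study drug until after the imaging visit. Nothing in the documents suggests that oxytocin alters head movement, so arm-related bias is a possibility to check, not an expectation.
- The nuisance sentence follows directly after a definition of two outlier types, intensity and motion. It can fairly be read as naming those two types. On that reading there is no global regression, and the plan already enters outlier terms.
- Brain activation is called a secondary endpoint in the abstract, but section 2.3 does not name it and Figure 3 has it only as a mediator. Section 2.5.3 presents mediation as exploratory.

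These limit the size of the point but do not remove it. The exclusion rule works as shown under either reading of the sentence, and realignment parameters are absent from the list under both.

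A reader might go further and infer that a shifted drug effect enters every activation result. The documents do not support that: a shift needs either movement that differs by arm, or global regression together with a drug effect on the global response. A reader might also infer that each 15 s food-cue block (5 × 3 s) is modelled as one impulse, with a large loss of signal. The text gives onsets and leaves duration unstated. One impulse per image, which the words also allow, keeps about 96% of the contrast signal-to-noise of a 15 s epoch. That is a matter of wording only.

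**Conclusion.** The concern holds as a gap in the stated imaging model. Runs with large gradual movement are normally kept, and no listed regressor represents that movement in the contrasts feeding the Aim 2 activation results and brain mediators.

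The main expected effect is loss of precision. Its size cannot be determined from the documents. The range of no gain (or a small loss) to about 40% of contrast SD rests on assumed drift, residual movement signal and noise, and the top of the range needs a 10 mm drift at the strongest assumed signal. Bias is conditional on movement changing differently by arm.

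The global-mean wording is ambiguous. It is harmful only if the time course is meant and oxytocin changes the global response to the contrasted conditions.

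The primary weight endpoint, the REE and caloric-intake endpoints, and their use as mediators do not depend on this model. This is a cheap improvement worth making, not a threat to the trial's main result.

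**What to change.** Amend section 2.5.2 before the imaging data are analysed:

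1. Enter the six realignment parameters of each run as nuisance regressors in the subject-level model for both tasks.
2. Report the number of runs with more than 3 mm of movement by arm and visit, and add a sensitivity analysis that excludes them. State whether the 3 mm is peak-to-peak range or displacement from a reference scan.
3. State that one indicator is entered for each ART-flagged volume, whether flagged on intensity or on motion, and that the global mean time course is not entered. If outlier volumes were all that was meant, this costs nothing.
4. As a clarification, state the modelled duration of the food-cue blocks and of the Stop-Signal trials.

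The cost is SAP wording and, if first-level models have been run, a re-run. No new data are needed. The downside is about 6 of 112 residual degrees of freedom per run (5%), and some loss of task signal where head movement follows the task blocks.

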¹¹ Division of Women's Health, Department of Medicine and Department of Psychiatry, Brigham and Women's Hospital and Harvard Medical School, Boston, MA, USA.

Abstract

Background: Obesity affects more than one-third of adults in the U.S., and effective treatment options are urgently needed. Oxytocin administration induces weight loss in animal models of obesity via effects on caloric intake, energy expenditure, and fat metabolism. We study intranasal oxytocin, an investigational drug shown to reduce caloric intake in humans, as a potential novel treatment for obesity.

Methods: We report the rationale, design, methods, and biostatistical analysis plan of a randomized, double-blind, placebo-controlled clinical trial of intranasal oxytocin for weight loss (primary endpoint) in adults with obesity. Participants (aged 18–45 years) were randomly allocated (1:1) to oxytocin (four times daily over eight weeks) versus placebo. Randomization was stratified by biological sex and BMI (≥ 30 to < 35 kg/m², ≥ 35 to < 40 kg/m², ≥ 40 kg/m²). We investigate the efficacy, safety, and mechanisms of oxytocin administration in reducing body weight. Secondary endpoints include changes in resting energy expenditure, body composition, caloric intake, metabolic profile, and brain activation via functional magnetic resonance imaging in response to food images and during an impulse control task. Safety and tolerability are assessed biweekly and at a 6-week follow-up after treatment completion.

Results: Sixty-one male and female participants aged 18–45 years were randomized (mean age 34 years, mean BMI 37 kg/m²). The study sample is diverse with 38% identifying as non-White and 20% Hispanic.

Conclusion: Investigating intranasal oxytocin's efficacy, safety, and mechanisms as an anti-obesity medication will advance the search for optimal treatment strategies for obesity and its associated severe sequelae.

Keywords: Obesity; Oxytocin; Weight loss; Appetite regulation; Energy metabolism; Neuroimaging

1. Introduction

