2.5.3. Statistical analysis plan

Figure 3 shows our statistical analysis plan. We will perform statistical analyses using R statistical software, and appropriate R packages [54]. For continuous endpoints (see 2.3.), we will apply mixed model regression for repeated measurements (MMRM). We will consider the between-group (oxytocin versus placebo) difference in the least-squares mean change of each individual endpoint variable from baseline to each follow-up study time point of interest as the response in MMRM; the change from baseline to week 8 study time point (end of treatment) will be of primary interest (see 2.3.). Treatment group (oxytocin versus placebo), study time point (visit), and treatment group*study time point interaction will be included as fixed factors in MMRM. The baseline value of the endpoint variable and stratification factors (biological sex, BMI) will be entered as covariates. Additional covariates may be considered as appropriate. The intercept and time slope of individual participants will constitute random effects. Parameters of MMRM will be estimated via restricted maximum likelihood (REML). Depending on the distributional characteristics of the data, we may apply logarithmic transformations and/or robust statistical methods. We will adjust for multiple comparisons where appropriate via the approach of Hothorn, Bretz, and Westfall based on single-step simultaneous inference using a joint multivariate t-distribution [55]. We will use a modified intention-to-treat approach for efficacy analyses, including all randomized participants with available data for at least the second baseline visit

(randomization/initiation of treatment) and the first on-treatment study time point. We will apply a per-protocol approach for sensitivity analysis, including only randomized participants who complete the study and demonstrate $\geq 80\%$ adherence to treatment. We will carefully examine patterns of any missing data regarding their relationships with the outcomes of interest and incorporate uncertainty due to missing data with multiple imputations where applicable.

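### The group-level fMRI comparison in 2.5.2 names no baseline or stratification covariates and, as written, is a change-score test that is usually less precise than a baseline-adjusted one

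*Combined protocol and SAP*

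**What the plan says.** Section 2.5.2 describes the group-level fMRI model in one sentence: "we will use a factorial design with baseline versus 4-week contrasts to examine changes in brain activation". The regions tested are three for the food cue task (VTA, OFC and anterior insula) and three for the Stop-Signal Task (dlPFC, dACC and preSMA). The sentence names neither the treatment factor nor the group-by-visit interaction, and no covariate. The only adjustment terms in that section belong to the subject-level model: "Global mean signal and motion outliers will be entered as nuisance regressors".

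Section 2.5.3 does have a covariate rule: "The baseline value of the endpoint variable and stratification factors (biological sex, BMI) will be entered as covariates". It belongs to the mixed model, whose scope is set at the start of the same section: "For continuous endpoints (see 2.3.), we will apply mixed model regression for repeated measurements (MMRM"). Section 2.3 does not list brain activation. Figure 3 shows it only in the mediator block, not among the endpoints. The Abstract, however, states: "Secondary endpoints include changes in resting energy expenditure, body composition, caloric intake, metabolic profile, and brain activation via functional magnetic resonance imaging".

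Table 2 places the scans at the second baseline visit (BL2) and at week 4, so each participant has one value before treatment and one on treatment. Randomization was stratified by sex and three BMI classes.

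**The concern.** With two visits, the group-by-visit effect of a factorial model is the difference between arms in mean change. That comparison subtracts the whole baseline value, noise included, whatever the correlation between scans. A model of the week-4 value with the BL2 value as a covariate subtracts only the part of the baseline that predicts week 4. In large samples it is at least as precise.

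Read literally, the plan therefore gives its other continuous endpoints a baseline- and strata-adjusted analysis and gives activation an unadjusted one, although all the needed covariates are collected. Aim 2 rests on this neural comparison, and the documents state no power for it. What is at stake is the chance of missing a real between-arm difference in the a-priori regions, and a reader's ability to tell which model will be fitted.

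**Working it through.** **Inputs from the documents.** 1:1 allocation; at least 50 evaluable of 61 randomized; 25 per arm and two-sided 0.05 (2.5.1); sex with two levels and BMI with three.

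**Assumptions, because the documents give no figure.** Correlation r between the BL2 and week-4 contrast values of 0.3 to 0.7; equal SDs at the two scans unless stated; N = 50 with usable scans at both visits. Runs can be excluded for motion, so N may be smaller.

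**The plan's own power figure.** It concerns weight, not fMRI. With 25 per arm, a difference of 3.2 kg and an SD of 4 kg, power is 80.7% by the normal formula and 79.1% by the t-test. The stated 80% reproduces. There is no corresponding fMRI figure to reproduce.

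**Variances of the treatment estimate**, with n per arm and common SD s:

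- Change score: (2/n) × 2(1-r)s²
- Adjusted for baseline: (2/n) × (1-r²)s²
- Ratio: (1-r²) / [2(1-r)] = (1+r)/2, so the information lost by the change score is (1-r)/2.

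**Cost of estimating covariates.** With k covariates the adjusted variance is multiplied by (N-3)/(N-3-k). At N = 50 this is 47/46 for baseline alone, and 47/43 for baseline, sex and two BMI-class terms. If the strata explain a share R² of the residual variance, it is also multiplied by 1-R².

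| r | 2(1-r) | 1-r² | Loss, baseline only, large sample | Baseline only, N = 50 | Full model, strata explain 0 | Full model, strata explain 10% |
|---|---|---|---|---|---|---|
| 0.3 | 1.40 | 0.91 | 35% | 34% | 29% | 36% |
| 0.5 | 1.00 | 0.75 | 25% | 23% | 18% | 26% |
| 0.7 | 0.60 | 0.51 | 15% | 13% | 7% | 16% |

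Example for r = 0.3: 1 - 0.65 × 47/43 = 0.29, and 1 - 0.65 × 0.90 × 47/43 = 0.36. A simulation of 8,000 trials with 25 per arm gave 34%, 22% and 14% for the baseline-only column at N = 50.

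**In terms of power.** For a single region value tested at an unadjusted 0.05, take an effect that the baseline-adjusted test detects with 80% power. The change-score test then has about 62%, 68% and 73% power at r = 0.3, 0.5 and 0.7. These figures show the relative loss. They are not the power of the plan's voxel-level, family-wise corrected tests.

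**Where the gain disappears.**

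- High correlation: with uninformative strata, the full model breaks even when (1+r)/2 × 47/43 = 1, that is r = 86/47 - 1 = 0.83. Above that it is slightly worse than the change score.
- Unequal SDs: if the week-4 SD is c times the baseline SD, the baseline-only loss is 1 - c²(1-r²)/(1+c²-2rc). For c = 1.25 it is 22%, 11% and 2% at r = 0.3, 0.5 and 0.7. For c = 0.8 it is 50%, 43% and 37%. At c = 1.25 and r = 0.7, charging the full covariate cost gives 0.981 × 47/43 = 1.07, so the adjusted model would be about 7% less precise.

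**The case against.** The strongest reply is that the absence of covariates is read from silence. Section 2.5.2 gives the group model one sentence and excludes nothing. The Abstract lists activation as a secondary endpoint, and 2.5.3 adds "Additional covariates may be considered as appropriate". The authors may well intend the same covariates for activation. This stands in part: a reader might infer that the plan has decided to ignore baseline and strata, and the documents do not support that. But the only group-level method stated is the visit contrast, and the only covariate rule points to a list of endpoints without activation. The text as written leads to the unadjusted comparison, and a clarification is needed either way.

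Second, the size is not a property of this trial. A reader might infer that 15% to 35% of the information is certainly wasted, or that this range measures the omission of baseline and strata together. Neither follows. The range is for baseline alone, under an assumed r and equal SDs. The contribution of the strata cannot be derived from the documents, and their degrees of freedom have to be charged.

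Third, the plan's inference is voxel- and cluster-based with family-wise correction. Replacing it with region averages and a new multiplicity rule would change what is tested and could dilute a focal effect. That is right, and neither step is needed to obtain the gain.

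Fourth, randomization keeps the change-score test unbiased. This stands in full.

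**Conclusion.** The point holds as one of efficiency and specification for Aim 2's neural comparison. As written, 2.5.2 yields a two-visit change-score test with no named group-level covariates, although a usually more precise analysis is available from data already collected.

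Over r = 0.3 to 0.7 with equal SDs, omitting the baseline costs 35% to 15% of the information. Compared with the full model at N = 50, the loss is about 29% to 7% if the strata explain nothing and 36% to 16% if they explain 10% of residual variance. At r of about 0.83 or above, or with a clearly larger week-4 SD, there may be no gain. The documents fix none of r, the SD ratio or the number evaluable for fMRI.

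Two further inferences should be resisted. The comparison is not biased, and the primary weight endpoint is untouched. Nor would the change below remove noise from the mediation analysis, because Figure 3 defines the mediator as the week-4 minus baseline change in activation.

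**What to change.** In 2.5.2:

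1. State the between-arm contrast explicitly as the treatment group-by-visit effect.
2. For each a-priori region, fit the week-4 contrast value on treatment, the BL2 value of the same contrast, sex and BMI class. Do this separately for fasted and fed in the food cue task, and for fasted only in the Stop-Signal Task. Alternatively, state that the covariate rule of 2.5.3 applies to activation in the regions of interest.
3. Keep the plan's own multiplicity correction and the SPM maps.

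This needs SAP wording and a short analysis script, but no new data. The statistical price is four degrees of freedom with BMI as three classes (baseline 1, sex 1, BMI 2), or three if BMI enters as a single continuous term. The mediator definition and the weight analysis stay as they are.
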